#### **3.20.1 Pilot Test One (Mothers)**

The mothers' research instruments were piloted with a group of 30 mothers with preterm infants in the NICU using the convenience sampling approach to determine the appropriateness and consistency of the questions. The questionnaire was provided in both languages, English and Malay, for better understanding in the Malaysian cultural setting. The pilot test also provided details about the approximate time needed to complete the survey. Participants were separated from the actual analysis so as to minimize the bias of measured effect. The data collected from the pilot test were not included in the final analysis of the study. The survey instruments were distributed to the respondents, with an explanatory note defining the aim of the research, and after a four-week interval, a repeat survey was conducted. This was to test instrument reliability and the KC booklet through a test-retest procedure.

The survey contained a blank space for feedback from the participants about clarification and the importance of the experimental group questions. Participants were questioned according to the items in the questionnaire, and after the pilot no significant changes were made. During

the interview all questions were read out in exactly the same way to all respondents. Then a teaching session was provided, primarily to test comprehension and clarity of content, and the information was evaluated. The return for the pilot test was 100% (n=30). On the basis of comments and feedback from the respondents, minor adjustments were made to rephrase the sentence structure in order to avoid ambiguities and misleading participants in responding to the knowledge items. Reliability was demonstrated, and construct and face validity was established.

The pilot study also included comments on the KCPR booklet for the control and experimental groups in order to assess the depth of understanding of the documentation provided after the instrument pilot was completed. The booklet was used as a form of self-observation for mothers in both groups on KC duration, weight gain and frequency of breastfeeding. The aim of this pilot study was to assess the feasibility of using the validated KCPR booklet to evaluate knowledge on understanding how to document daily KC duration and weight gain. This study also aimed to examine the efficacy of KC's structured standard evaluation method in relation to preterm infant outcomes, in particular, the duration of KC performance, breastfeeding rates, and length of hospitalization (LOS). Data from 30 mothers who met the study criteria were collected from November 2017 to January 2018. Based on comments from the pilot study and feedback on outcomes, the instructions on the duration of KC, to be performed 1 hour per day and 4 to 5 hours per week (16 to 20 hours per month) were simplified. Therefore, compliance with the duration of KC was classified according to groups in relation to the amount of KC performed. The groups for KC duration were classified into Group 1 (did not provide KC), Group II (1 hour to 5 hours per week), Group III (6 hours to 10 hours per week), Group IV (11 hours to 15 hours per week), Group V (16 hours to 20 hours per week) and Group VI (more than 20 hours per week). Other than that, the KC guidelines and protocol were simplified in the flip chart provided, with the aim of

increasing mothers' understanding of the benefits of KC and the quality of premature infant care practice. The alpha reliability was calculated with Cronbach's Alpha, which was between 0.78 - 0.95 for each of the four constructs as displayed in Table 3.16. The Content Validity Index of the KCQ Bahasa Malaysia version was 0.95, which was considered appropriate. The final versions of the instruments are set out in Appendices A and B.

Table 3.5: Cronbach's Alpha and KR20 Measure Reliability for Mothers' Instruments.

Items	Alpha values	Number of items
a) Perception	0.813	20
b) Knowledge	0.785	11
c) Barriers	0.873	19
d) Stress	0.951	7

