- e. Advocate for mothers to perform kangaroo care at least 1 hour a day and accumulate to 4 to 5 hours a week until 3 months of age. Evidenced by Kangaroo Care practice.

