## 3. State the benefits of kangaroo care to infant-mother dyads.

Why should I perform Kangaroo Care?

Babies and mothers get a lot of benefits:

*3.1 For infants;*

- i) Increases the sleep of infants, which can enhance weight and brain development.
- ii) Controls temperature, heart rate, and respiration for infants.
- iii) Supports successful breastfeeding sessions and reduces infection.
- iv) Shortens the length of hospital stay.

*3.2 For mothers;*

- i) Increases confidence in ability to care for babies.
- ii) Enhances bonding, feeling of closeness with babies.
- iii) Improves mothers' milk production.
- iv) Creates more nurturing interactions.

4) Explain the kangaroo care technique.

*Who can perform Kangaroo Care?*

Mums should do it. Every medical situation at NICU, however, is different. So ask your nurse, if your infant is a successful candidate indeed. If you can't do KC or don't feel confident, don't worry. But there are plenty of ways to help and take care of your infant. Speak to your nurse.

*When can I perform Kangaroo Care?*

You can perform at any time between 90 to 120 minutes after feeding. Schedule a suitable time with your nurse and set aside at least 1 hour or 60 minutes a day, and plan to sit 4 to 5 hours a week with your baby. Please feel free to ask a member of the NICU team for further information.

5) State the preparation before, during and after the KC procedure.

*How do I perform Kangaroo Care?*

You're going to dress your baby up in a diaper and head cap. Your baby should be positioned upright between your breasts. Have its tummy against

your chest. Head turned to one side, arms and legs in a bent position.

Support your baby's head, back and buttocks. [Please refer to Appendix O (a) and O(b)].

Ludington-Hoe,et al.(1990,2013,2018) & Nqyist,(2010)

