R: To keep baby warm.

n) Advise mother to be in KC position not less than 1 hour. Accumulatively continue KC for 4 to 5 hours a week and until the infant is 3 months old.

R: To complete the cycle of sleep.

o) Help the mother to initiate breastfeeding after the baby shows readiness and signs of feeding cues; moving tongue and mouth, licking the mother's skin during KC procedure.

R: To encourage partial or exclusive breastfeeding.

p) Tidy up the mother and equipment.

R: For comfort and cleanliness.

(United States Institute of Kangaroo Care, 2018)

4. *Documentation in kangaroo care record progress (KCPR) booklet.*

- Record the date, time, temperature, duration from time KC commences until

completion of the session, weight gain, and type of feeding intake daily in the KCRP booklet provided.

R: To monitor the frequency of KC, weight gain, and breastfeeding rates.

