### **3.14.3 The Kangaroo Care Progress Record (KCPR) booklet.**

The creation of this booklet was based on the results of Phase I and adapted from the original article by Singh, Amritanshu, & Mukherjee (2014) and Biswas, Malpani & Ekka (2016) to fulfill the study's objectives. This was to ensure that the booklet for KCRP was suitable for mothers in the local context. The KCPR booklet was prepared in English and Malay language, with a table for date, time, length of KC, weight gain, and mode of breastfeeding. It also helped the mothers to gain information about the KC technique and its benefits. This KCPR booklet provided a motivational resource, particularly for mothers who were unable to visit the NICU on a daily basis and who were thus able to prepare for their next visit to provide KC for their premature infant so as to maximize KC implementation to between four (4) to five (5) hours in a week. The following information was included in the KCPR booklet.

In addition, premature infant mothers need to learn about the KC technique, the effects of KC, the average implementation of hours of KC per day, the devices used by the premature infant for the kangaroo care technique, premature infant growth, and premature infant nutrition up to the first 3 months. The KCPR booklet was limited to 30 pages in order to avoid information overload. Upon amendment, consent was given by all meeting committees, which consisted of two (2) senior nursing lecturers, one (1) matron in charge of the department and one (1) sister. The KC-EP for the mothers in the experimental group and the KCPR booklet were then sent to one neonatologist and one matron in charge of verification. The neonatologist and the matron in charge were invited to ensure that the module contents designed were compatible with the clinical and institutional needs. The KC-EP developed for mothers and the KCPR booklet were then given to four (4) mothers whose preterm infants were admitted to the NICU and five (5) NICU nurses who were not directly involved in the development of the KC-EP in order to verify the readiness of the KCPR booklet. There were no major issues raised by the two neonatologists and the matrons. The evaluation results showed that the evaluators, the four (4) mothers and five (5) nurses, could understand the contents of the KCPR booklet.

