## Documentation

- The diary for the infant progress on
- KC frequency – 1 hour per day and 4-5 hours per week in the first 3 months old
- KC attainment of breast feeding nearly exclusive
- Weight gain monitored in every 1 month and 3 months old of corrected ages.

45

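### The KC compliance bands have no cut at 4 h/week, the lower limit of the prescribed dose, and the study material states two different weekly targets

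*Combined protocol and SAP*

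**What the plan says.** Section 3.20.1 (Pilot Test One) reports that, after the pilot, the instruction on KC duration was simplified: "to be performed 1 hour per day and 4 to 5 hours per week (16 to 20 hours per month"). It then classifies compliance with that duration: "The groups for KC duration were classified into Group 1 (did not provide KC), Group II (1 hour to 5 hours per week"), Group III 6-10, Group IV 11-15, Group V 16-20 and Group VI above 20 hours per week.

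Most of the protocol gives the same weekly dose:
- Section 3.11, mothers' programme, aim e: "at least 1 hour a day and accumulate to 4 to 5 hours a week until 3 months of age".
- Section 3.11, theory module, on when to perform KC: "plan to sit 4 to 5 hours a week with your baby".
- Section 3.11, practical session, step n: "Accumulatively continue KC for 4 to 5 hours a week and until the infant is 3 months old".
- Section 3.14.3, describing the purpose of the record booklet: "maximize KC implementation to between four (4) to five (5) hours in a week".
- Appendix P, theory slide headed Documentation: "1 hour per day and 4-5 hours per week in the first 3 months old".
- Sections 3.15 (aim e), 3.16.2 and 3.16.4(a) agree.

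Four pieces of teaching material give 7 hours a week instead: the English flipchart (Appendix O(a)), the Malay flipchart (Appendix O(b)), the sitting-transfer slides (step 14) and the standing-transfer slides (step 19, on a slide that appears twice). A further Appendix P slide, giving a general definition of KC, says at least 5 hours a week.

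Table 3.4 lists KC compliance under weight gain, in hours/weeks, and under breastfeeding. Both rows carry frequency and percentage, a continuous-data label, and mean and SD among the descriptives.

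**The concern.** Section 2.6 criticises earlier studies for not reporting adherence and makes compliance rates an aim. Section 1.4 links infant outcomes to compliance with KC practice. The natural question is what share of mothers gave the prescribed dose. The only compliance classification in the documents cannot answer it, because the one boundary near the dose lies above it (between 5 and 6 h) and none lies at its lower limit.

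The second part concerns what the dose is. If the protocol asks for 4-5 h and the flipchart for 7 h, a compliance percentage means little until the target behind it is named.

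**Working it through.** **Inputs.** Dose 4-5 h/week, 16-20 h/month, and the bands (section 3.20.1). Daily minimum of 1 h (section 3.11, aim e). Flipchart and transfer-slide target of 7 h/week (Appendices O(a) and O(b); transfer slides). Recruitment at 28 to 36+6 weeks (section 3.7.1). T2 at week 52 (Table 3.2(b)).

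**The plan's own figure.** Monthly dose = weekly dose × 4 weeks: 4 × 4 = 16 and 5 × 4 = 20. The stated 16-20 h/month reproduces.

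**Bands against the dose.** The lower limits of the bands are 0, 1, 6, 11, 16 and above 20; none is 4.

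| Weekly hours | Group | Against 4-5 h/week |
|---|---|---|
| 1, 2, 3 | II | below |
| 4, 5 | II | at dose |
| 6, 7 | III | above |

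Three of the five whole-hour values in Group II miss the minimum and two meet it. A mother at 1 h/week gives 1/5 = 20% to 1/4 = 25% of the dose and shares a group with one who gives all of it.

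**What the bands can show.** Everyone in Groups III-VI exceeds 4 h, and everyone at 4 h or more is in Groups II-VI. So:

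share in III-VI ≤ share at or above 4 h/week ≤ share in II-VI.

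The width of this interval is the share in Group II, the band that contains the target.

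**The two weekly targets.** 7/5 = 140% and 7/4 = 175%, so the flipchart asks for 140-175% of the protocol's weekly dose. In reverse, 4/7 = 57% and 5/7 = 71%: a mother at the protocol dose reaches 57-71% of the flipchart's figure. Seven hours is in Group III.

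**The daily instruction.** 1 h × 7 days = 7 h/week. The daily minimum, followed literally, gives the flipchart's total. A total of 4-5 h corresponds to one-hour sessions on four or five days.

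**From weekly totals to one group.** Follow-up from recruitment to T2 runs from 52 − 36.86 = 15.1 to 52 − 28 = 24 weeks. Section 3.20.1 does not say how 15 to 24 weekly totals become one group per dyad.

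**The case against.** The strongest reply is that little depends on the bands. They appear only in the pilot section. Section 3.19 attaches no test or table to them. No specific objective (1.5.2) or hypothesis (1.6) rests on compliance. Table 3.4 labels the compliance rows as continuous data with mean and SD, section 3.16.2 collects hours per week, and the sample booklet page in Appendix O(a) has start and end times. Equal-width bands are also a defensible description of exposure, since control mothers could do KC if interested (section 3.16.1). All of this stands and limits the point to the compliance results. It does not supply a threshold for having met the dose; none is given anywhere.

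The 7 h figure also has a coherent reading: full daily practice, matching the guideline cited in section 3.16.4, with 4-5 h as the accepted total. Section 3.14.3 links 4-5 h particularly to mothers who cannot visit daily. That is plausible, but the plan does not say it.

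A reader might infer more than the documents support:
- *That the weight-gain or length-of-stay comparison is damaged.* Those outcomes are compared between groups and do not use the bands.
- *That compliance information is lost.* The hours are recorded and can be re-cut.
- *That some mothers were taught 4-5 h and others 7 h.* The flipchart illustrates points within the same programme, and section 3.14.5 describes sessions meant to give everyone the same information. The module's pointer ("Please refer to Appendix O (a) and O(b")) follows the item on positioning, not the one on timing.
- *That the booklet prints 4-5 h.* Section 3.14.3 is protocol prose about the booklet; the data sheet in Appendix F(b) shows no weekly target.
- *That mothers between bands, such as at 5.5 h, cannot be classified.* The limits are whole-hour labels and sessions are one hour; ordinary rounding closes the gaps.
- *That the bands were meant per month, since 16-20 is both Group V and the monthly dose.* Every band from II to VI is labelled per week.

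**Conclusion.** The point holds, as a cheap improvement. Group II combines mothers below the prescribed weekly dose with mothers at it, so a table of the bands bounds the share who met the dose but does not give it. The material also carries two weekly targets, 4-5 h and 7 h, and the daily-hour instruction agrees with the second.

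The effect is confined to compliance results. Within these, the uncertainty from the bands equals the share of mothers in Group II. How many of the 48 experimental mothers that is cannot be derived from the documents. The conclusion takes the bands as printed, in hours per week with whole-hour limits, and treats 4 h/week as the minimum that counts as meeting the dose.

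**What to change.** 1. State one weekly target and how it relates to the daily hour, for example one-hour sessions on at least four to five days a week. Changing only the weekly number on the flipchart would leave its daily-hour instruction unreconciled.
2. If the flipcharts and transfer slides are still to be used, align them with that target. If they have already been used, as the data-collection dates in section 3.16 suggest, disclose the 7 h wording.
3. In section 3.19 or Table 3.4, define compliance as total recorded hours divided by weeks from recruitment to T2. Report the percentage at or above 4 h/week, and at or above 7 h/week if the flipchart was used.
4. If bands are kept, use 0, >0 to <4, 4 to 5 and >5 h/week.

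The cost is a small amount of re-tabulation, a sentence or two in the analysis section and, where still useful, minor edits to the flipcharts and transfer slides. No new data are needed.

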### 3.20.2 Pilot Test Two (Nurses)

A group of 50 nurses was chosen, using the convenient sampling method, as the pilot test for the research instrument from 23rd of November 2017 until the 26th of November 2017 during a continuous education program at the KL International Neonatology Conference (KLINC) in Kuala Lumpur to assess questionnaire appropriateness and clarity. The pilot test also provided details about the approximate time required to complete the surveys. Participants were excluded from the real study to reduce the bias of measured effect, and data obtained from the pilot study were not included in the final analysis. The survey instruments were distributed to the respondents, together with an information sheet describing the purpose of the study. A blank space was provided for feedback from participants on the clarification and quality of the questions for the experimental group. Interviewees were questionned according to the items in the questionnaire, and after the pilot no significant changes were made.

During the interview sessions the questionnaires were read out to all participants in precisely the same manner. The teaching session was provided once, mainly to evaluate comprehension and clarity of content, and testing of knowledge and compliance was conducted. The pilot test return was 100% (n=50). Based on the results of the pilot study and feedback from the nurses, minor changes were made to redo the sentence construction to prevent misunderstandings and misleading participants in responding to the items on knowledge and ventilators. More detailed instructions concerning the provision of the experimental group remained unchanged, as reliability was demonstrated and constructed, and face validity was established. Other than that, the steps in the procedure for sitting and standing transfers in the KC guidelines were simplified, with the aim of increasing nurses' understanding of KC procedure and the skills to be practiced. The data, presented in Table 3.15, were collected and there was a Cronbach's Alpha reliability of between 0.79 - 0.90 for each of the five constructs as follows:

Table 3.6: Cronbach's Alpha and KR20 Measure Reliability For Nurses' Instruments.

Items	Alpha values	Number of items
a) Perception	0.880	25
b) Knowledge	0.793	20
c) Practice	0.841	11

### 3.20.3 Measure

The researchers used Arthur J. Angler & Eileen Brumbaugh et al., (2013)'s modified Kangaroo Care Questionnaire Survey (KCQs) and adopted the Parental Stress Scale: Neonatal Intensive Care Unit (PSS: NICU: P&R) from Mile et al., (1999). The questionnaire consisted of 14 basic characteristics of mothers with premature infants and a total of 57 items to assess mothers' perception, knowledge, and perceived barriers in relation to kangaroo care

and their stress levels. Blind forward and backward translation of the questionnaire from English to Bahasa Malaysia was carried out. Both the forward and backward translated data were checked against the original questionnaire to see if any inconsistencies would require further review (Jones, 2001; Wild, 2005).

The researchers used the modified Kangaroo Care Questionnaire (KCQ) established by Arthur J. Angler & Eileen Brumbaugh et al., (2013) for the nurses. The questionnaire consisted of nine participant characteristics and a total of 56 items to evaluate the perception, knowledge, and practice of KC among nurses. Both forward and backward translated questionnaires were checked against the initial questionnaire to see if any differences needed further verification (Jones, 2001; Wild, 2005).

### **3.21 Summary**

This chapter provides explanations of the methods and design used in this study to respond to the research questions. Also presented were explanations of the research principles, samples, settings, instruments, procedures, and statistical analysis. The next chapter will discuss the study's findings.

### **PER: PERMOHONAN KEBENARAN UNTUK MENJALANKAN PENYELIDIKKAN KEJURURAWATAN DI NEONATAL INTENSIVE CARE UNIT (NICU), JABATAN PAEDIATRIK, PUSAT PERUBATAN UNIVERSITI MALAYA**

Perkara di atas adalah dirujuk. Sehubungan dengan perkara tersebut di atas, saya [name], pelajar Phd dari Jabatan Sains Kejururawatan Universiti Malaya ingin memohon kebenaran untuk menjalankan penyelidikan di hospital tuan.

2. Tujuan penyelidikan adalah untuk memenuhi keperluan pengijazahan program Doktor Falsafah, Universiti Malaya.

3. Berikut adalah butir-butir mengenai penyelidikan yang akan dijalankan:

3.1 Tajuk : The Effectiveness of Kangaroo Mother Care Among Mother With Premature Infant in NICU.  
3.2 Tujuan : The purpose of the study is to evaluate whether a specific teaching program on Kangaroo Care (KC) has significant effects for the infant and the mother.  
3.3 Metod kajian : A quasi-experimental and longitudinal design study (Intervention and questionnaire based)  
3.4 Target populasi: The mother – infant dyads and all nurses in NICU, UMMC.  

## Appendix C : Letter for Approval from Head of Nursing (NICU)

27hb Julai 2017.

Pengarah,  
Pusat Perubatan Universiti Malaya,  
[name],  
[name].

Ketua Jururawat,  
Neonatal Intensive Care Unit (NICU),  
Pusat Perubatan Universiti Malaya,  
[name],  
[name].

Melalui: [name] [name] [name]  
Ketua,  
Jabatan Sains Kejururawatan.

Tuan,

[figure not shown]
**PER: PERMOHONAN KEBENARAN UNTUK MENJALANKAN PENYELIDIKKAN  
KEJURURAWATAN DI NEONATAL INTENSIVE CARE UNIT (NICU), JABATAN PAEDIATRIK,  
PUSAT PERUBATAN UNIVERSITI MALAYA**

Perkara di atas adalah dirujuk.

Sehubungan dengan perkara tersebut di atas, saya [name], pelajar Phd dari Jabatan Sains Kejururawatan Universiti Malaya ingin memohon kebenaran untuk menjalankan penyelidikan di hospital tuan.

2. Tujuan penyelidikan adalah untuk memenuhi keperluan pengijazahan program Doktor Falsafah, Universiti Malaya.
3. Berikut adalah butir-butir mengenai penyelidikan yang akan dijalankan:
  - 3.1 Tajuk : The Effectiveness of Kangaroo Care Among Mother With Premature Infant in NICU.
  - 3.2 Tujuan : The purpose of the study is to evaluate whether a specific teaching program on Kangaroo Care (KC) has significant effects for the infant and the mother.
  - 3.3 Metod kajian : A quasi-experimental and longitudinal design study (Intervention and questionnaire based)
  - 3.4 Target populasi: The mother – infant dyads and all nurses in NICU, UMMC.
  - 3.5 Masa kajian : August 2017 till September 2019
  - 3.6 Supervisor : [name] [name] (Clinical Supervisor)  
: [name] [name] [name] (Supervisor Nursing Aspect)  
: [name] [name] (Supervisor Methodology Aspect)
4. Bersama-sama ini, disertakan satu salinan surat kebenaran daripada Ethics Committee untuk semakkan pihak tuan. Segala pertimbangan dan kerjasama daripada pihak tuan amatlah saya hargai dan didahului dengan ucapan ribuan terima kasih. Sekian.

Yang benar,

([name])

Pelajar PhD,  
Fakulti Perubatan,  
Jabatan Sains Kejururawatan,  
Universiti Malaya.

